Protocol Title: Study of Colorectal Cancer Screening Options

Study Protocol: 5/09/2019

PI: [name]

NCT05987709

1. Protocol

Title: Study of Colorectal Cancer Screening Options

PI: [name]

2. Objectives

We propose to evaluate Guardant Health's commercially available colorectal cancer screening assay (Guardant SHIELD) in individuals who are not up to date with CRC screening.

Primary Objective (or Aim)

Assess colorectal cancer screening completion among patients who are non-adherent after receiving stool test outreach, who have an upcoming clinical appointment, and who are offered a commercially available colorectal cancer blood test versus usual care (i.e. reminder to complete stool testing during their clinical appointment).

Secondary Objectives (or Aim)

Assess patients' and providers' perceived confidence in the test (based on available test performance characteristics) and willingness to obtain/offer the test on an on-going basis, based on qualitative interviews; assess preliminary rates of follow-up colonoscopy completion (after an initial abnormal test result) among participants allocated to the blood test vs. usual care condition.

3. Background Information and Rationale

Blood-based tests for colorectal cancer detection are thought to offer many advantages over stool-based and endoscopy-based tests. Such tests can be easily completed during in-person clinic visits and can be combined with other blood draws. Such tests may be particularly acceptable for patients who forgo stool-based testing options due to the 'yuk' factor. While blood-based tests will likely produce greater colorectal cancer screening adherence than stool-based testing and endoscopy options, there is little empirical data to support this claim.

4. Study Design

The study will be a randomized clinical trial comparing the two options for colorectal cancer screening: the commercially available blood test and usual care (reminder to complete FIT). Patients will be randomized (1:1) to receive the offer of a commercially available blood test (intervention) or usual care. Only intervention patients will be consented to the study. Consented patients will be asked to complete a blood draw at the Kaiser Permanente Northwest (KPNW) clinical lab. Our primary analysis will compare rates of colorectal cancer screening (we will consider completion of the blood draw as completion of colorectal cancer screening) in the two study conditions using intention-to-treat data; we will also report the proportion of intervention participants who consent and, among those, the proportion who successfully complete the blood draw.

We will also conduct qualitative interviews with 20-30 intervention patients and/or providers to understand perceived confidence in the blood test and willingness to receive/offer it on an every-three-year basis. Patients will have been offered the blood test option and will have completed the blood test (completers) or have agreed to take part in the study, but did not show to the blood test visit (non-

completers). Providers will be involved in offering colorectal cancer screening to patients and following up on abnormal results, such as primary care providers and GI specialists.

5. Study Population

a. Number of Subjects

We will prospectively identify and recruit 400 patients from KPNW who received, but did not complete, a FIT in the past 3-9 months, and have an upcoming appointment at a KPNW clinic (within 2 – 6 weeks of eligibility determination). Patient identification will be performed on a weekly basis by a CHR analyst. We will overrecruit by up to 10% to account for participant no-shows and screen-failure.

For the qualitative interview component of this study, 20-30 intervention patients and/or providers will be interviewed.

b. Eligibility Criteria

Inclusion Criteria:

- Age 45-75
- Received a FIT test in the last 3-9 months yet did not return their FIT
- Upcoming appointment or willing to reschedule an appointment at KPNW within 2 - 6 weeks
- Able and willing to provide informed consent if in the intervention arm

Exclusion Criteria:

- On do not contact list
- Having a legal authorized representative
- Non-English speakers

c. Vulnerable Populations

Vulnerable Populations (VPs)	Include/Exclude	Rationale
Pregnant women	Include	Pregnant women aged 45-75 are still eligible for colorectal cancer screening; there are no unique risks to obtaining a blood test among pregnant women.
Children	Exclude	Colorectal cancer screening is not recommended among individuals younger than 45.
Neonates of uncertain viability or nonviable neonates	Exclude	Colorectal cancer screening is not recommended among individuals younger than 45.
Prisoners*	Excluded	The KPNW IRB does not have the appropriate membership to review research involving prisoners.

Other VP	Rationale for Inclusion
Limited English proficiency	We will exclude patients whose language preference is a non-English language.
Decisionally impaired adults	We will exclude patients with a diagnosis of dementia (documented in the electronic health record).

Click or tap here to enter text.

d. Setting

This is not a multi-site study. Study activities will take place at Kaiser Sunnyside Medical Center and KPNW Center for Health Research.

For the qualitative interview component of this study, the interviews with both patients and providers will be conducted via telephone using password encrypted devices and software (e.g. CHR laptop using Microsoft Teams calling functions).

e. Recruitment Methods

The CHR analyst will identify patients eligible for recruitment based on the eligibility criteria outlined above.

1. The eligible population will then be randomized (1:1); randomization will be stratified based on age group (45-49, 50-64, 65+) and colorectal cancer screening history (ever vs. never).
2. Once the patient list has been identified by the analyst, the population will be uploaded into Clinical Conductor for use by research staff to conduct outreach.
3. The research staff will outreach to the patients for recruitment by mail and/or email. The research staff will send an introductory study letter/email and a copy of the consent form to participants allocated to the intervention condition. Research staff will then call the patient for recruitment.
 - a. A maximum of three calls will be made
4. Research staff will coordinate meeting the patient prior to or after their clinical visit.
5. Outcomes of patient contacts will be tracked (declined, not able to reach, etc.) outcomes into Clinical Conductor.
6. The project analyst will pull data when the project is complete.
 - a. From clinical conductor
 - b. From Virtual Data Warehouse (VDW) datasets

For the qualitative interview component of this study, for patient completers of the blood test, we will identify a list of recent completers and reach out via letter and/or email. These

possible interviewees will have been informed of the possible interview at their initial consenting process when participating in the blood test.

For non-completer patients, we will generate a list of those who agreed to participate but did not show for their blood collection visit and reach out via letter and/or email.

In both cases, qualitative staff will follow up with up to 3 phone call attempts to ascertain willingness for the interview or not. The recruitment letter/email provides individuals with study team contact information through which they can opt-out of further contact or outright decline.

For provider interviews, we will work with the CHR study PI and study analysts to generate a list of primary care and GI providers who are involved in offering CRC screening and follow up surveillance. Providers will be sent an email request and study staff will follow up by email or phone up to 3 times to ascertain interest in the interview.

f. Consent

Written consent will be obtained prior to any study procedures, for patients in the intervention arm.

An IRB waiver of informed consent will be obtained for patients in the usual care group. Usual care patients will not be asked to sign informed consent, as it may create unnecessary confusion. Outcome data will be collected through retrospective chart review for participants in both study conditions.

For the qualitative interview component of this study, we request a waiver of *signed* informed consent. Verbal consent will be obtained from the patients and providers for participation in the qualitative interviews.

Informed Consent Process

Patients will be mailed and/or emailed copies of the consent forms prior to the research visit so that they can be thoroughly reviewed and discussed with family and friends, if they choose. Patients are also given contact information so that they can contact research personnel by telephone throughout the study. Patients will be interviewed and consented in private. All discussions with patients will be held in strictest confidence and out of earshot of the general public.

Patients will be fully informed that their participation in the study is voluntary. Patients may decline to be part of the study. Their decision to participate in the study will not affect the care they receive.

For the qualitative interview component of this study, informed consent will be obtained from the patients and providers utilizing an information sheet and consent discussion, but without signed documentation. If, after the consent discussion, an individual agrees to be interviewed their verbal agreement will be documented by study staff. This research does not involve procedures for which

written consent is normally required outside of the research context. This study presents no more than minimal risk of harm to subjects.

Non-English-Speaking Subjects

N/A

Assent of Children and Parent Permission

N/A

Adults Unable to Consent/Decisionally Impaired

N/A

g. HIPAA Authorization – if study will use or disclose Protected Health Information (PHI)
Signed HIPAA Authorization will be obtained from each patient allocated to the blood test intervention. The authorization will be combined into the informed consent form.

Waiver or Alteration of HIPAA Privacy Rule Authorization

For the usual care group, we request a Waiver of HIPAA authorization.

For the qualitative interview component of this study, we request an alteration of HIPAA authorization, removing the requirement for signature. Verbal authorization will be obtained.

6. Communicating with Recruits and Participants

Study staff may call, email, and/or text message potential participants (i.e. recruits) ahead of their scheduled consent and blood draw visit to remind them of their appointment.

In addition, study staff may generally correspond with individual participants or recruits by phone or back and forth email and/or text messaging to address participant questions, concerns, or to coordinate scheduling or meeting up for their visit. Back-and-forth communication by email or text messaging will not be required. Participants will be offered another way of communicating with staff, such as by phone, in case they do not feel comfortable exchanging information over email and/or text. Sensitive study content or protected health information (PHI) will not be included in these emails or texts. A potential participants willingness to take part in back-and-forth communication by email and/or text messaging will be documented in their research record.

7. Study Procedures

Blood Sample Requirements

1. One (1) blood sample will be collected in each of 200 unique patients who (a) received, but did not complete, a FIT in the past 3-9 months, and (b) have an upcoming appointment at KPNW in the next 2-6 weeks.
2. Forty (40) mL of whole blood will be collected per sample using 4, 10mL Streck tubes as part of the Blood Collection Kit ("Kit") provided by Guardant.

3. Guardant's Test Requisition Form (TRF) will be completed (with the PI information and participant ID number) for each sample and placed in the Kit.
4. Each sample will be packaged and the corresponding TRF included in the Kit. The Kit will be shipped to Guardant overnight using the pre-paid, pre-addressed FedEx Clinical Pak.
5. Samples received by Guardant greater than 7 days from the time of receipt may be subject to cancellation per the CLIA-certified lab protocol.

No identifiable patient information will be placed on the tube – Only a study sample ID will be on the tube when sent to Guardant Health's lab.

Blood Sample Processing (CLIA line)

Once received Guardant will test the blood samples. Guardant will test samples using its colorectal cancer screening assay in its CLIA-certified lab. A final report for each sample will then be provided to the investigator(s) via its online portal within approximately 14 days of sample receipt. Guardant will cover the cost of processing and reporting up to 200 tests.

Data Collection

The study analyst will provide certain clinical data to Guardant (within 120 days of the 200th intervention patient enrolled, and blood sample received), the details of which follow:

- Patient ID
- Age at study entry
- Cohort assigned to
- GH colorectal cancer screening test result (if applicable)
- FIT test result after randomization (if applicable)
- Time between colorectal cancer screening test result offer and screening test completion
- For those with positive screening test, was colonoscopy completed?
 - If yes, time between positive test result and colonoscopy
 - If yes, colonoscopy outcome (CRC, advanced neoplasia, non-advanced neoplasia, negative, incomplete)

Qualitative Data Collection

Qualitative interviews will be conducted among a subset of patients who have (completers) and have not completed (non-completers) the blood test and among providers (20-30 total interviews) who offer colorectal cancer screening to patients. Each participant will undergo a single interview, conducted via telephone, that will last for 45-60 minutes. Each interview will be audio recorded with participant consent.

a. Data Analysis

Data analysis will be conducted at KP CHR will guidance from the statistician at Guardant Health.

Below is a list of primary and secondary endpoints for analyses.

1. Primary endpoint:
 - a. Colorectal cancer screening completion (incl. blood test, stool-test or colonoscopy) rate within 3 months of randomization, by study condition (using intention-to-treat design).
2. Exploratory endpoint:
 - a. Percent of individuals offered blood-based testing who accepted, percent who complete the test.
 - b. Test positivity rate, % of positive individuals who proceeded to diagnostic endoscopy

For those with endoscopy, percent with findings (colorectal cancer, adenoma, negative). Exploratory endpoints will not be statistically powered for comparisons.

Sample size calculation:

Sample size was calculated based on a previous study (Liles, et al 2016). Assuming that the adherence rate of FIT is 88%, a sample size of 200 in each group (FIT and blood test) achieves 91.8% power to detect an adherence rate difference of at least 8% between the two groups.

b. Qualitative Analysis

All interview recordings will be transcribed verbatim. All transcribed interviews will be coded using thematic data analysis and the constant comparative method to identify patterns in interviewees' responses. Code books will be developed for the patient and clinical staff interviews based on an initial review of the transcripts, and the interview guide questions. Codes will be applied to transcripts with the aid of a qualitative software program (e.g., ATLAS.ti) or using a template built in excel. Coding will be an iterative process with the goal of identifying connections and patterns across participants' responses. Emergent themes from the interviews will help us understand both patient and provider acceptability of the blood test as a CRC screening method, and aid in identification of barriers and facilitators to implementing the blood test option within a health system.

c. Sharing of Results with Subjects

Results from the commercially available blood test will be provided to the patient (through mail/email or phone call). A copy of the final report will be scanned into the patients EMR. In addition, participants whose test result is abnormal will be notified by the GI department, whose staff will facilitate the referral and scheduling of a follow-up colonoscopy (a recommended screening at KPNW). Participants whose tests result is normal will receive a letter that includes a number to call if they have any questions.

The blood sample will only be tested for markers of colorectal cancer; there is no known risk of incidental findings. The laboratory conducting the test is Clinical Laboratory Improvement Amendments (CLIA) certified.

d. Data and/or Specimen Banking
 N/A

8. Privacy, Confidentiality and Data Security

Information obtained in this study will include protected health information of the patients. The identity of the patients will not be part of the study. No personally identifiable information will be shared outside the clinic. All reports, forms, or articles related to this study will be prepared such that no individual patient can be identified. Samples will be coded with a study ID number to protect patient confidentiality. Only the authorized CHR study personnel will have access to the link between the patient's identifiable information and the study ID.

Collection of sensitive data will not occur as a part of this study.

Describe the plan for storage of data and/or specimens.

In order to minimize the risk of loss of confidentiality, all records related to study data will be kept in locked cabinets. Access to study information will be restricted to authorized research personnel. A password system will be used to control access to all information stored on a secured computer. All residual blood samples will be discarded at the end of the study.

For the qualitative interview component of this study, the interviews with both patients and providers will be conducted via telephone using password encrypted devices and software (e.g. CHR laptop using Microsoft Teams calling functions) and stored behind CHR firewalls within project specific folders. De-identified audio transcripts will be retained indefinitely.

Study data will be retained and destroyed in compliance with the study contract.

Collection of data from subjects electronically

N/A

Does this study involve the disclosure of PHI to a collaborator?

Data for this study will be disclosed to Guardant Health (the funder). In addition to the blood samples sent to Guardant, they will also receive:

- A limited dataset of patient characteristics
- Data will be limited, and identifiers removed. Guardant Health will not receive any Personal Health Information
- Data will be transferred via Secure File Transfer site.

Data Commitments (data and specimen sharing)

Recipient and Description of Materials	Identifiers* (note w/an X)	Health Information** (note w/an X)	HIPAA Documentation (see policy NWRC.PRIV.04)
Guardant	 Fully Identifiable	 Yes	 Signed Authorization

**Protocol Template
(Use with Core Data Form)**

Form

NCRSP HRP FORM KP-202, Version 1.2
KP NW Implementation Date: 05/09/2019
Page 9 of 10

Blood specimens and a patient characteristic dataset will be sent to Guardant.	 Limited Data Set  De-Identified  Aggregate	 No	 Waiver of Authorization  Limited Data Set only (DUA Required)  De-Identified or Aggregate Data  N/A, No Health Information
--	--	-----------------------------	---

9. Provisions to Monitor Data to Ensure the Safety of Subjects

Because this study will not involve treatment, adverse events are unlikely to occur. However, as a safeguard, the clinical research coordinators, and the principal investigator will review study data; study results (when available); complaints about the research; and will report any adverse events or unanticipated problems involving risk to patients to the Institutional Review Board. Adverse Events of any sort reported to the project team and investigator will also be characterized by type and number. Standard risks associated with blood draws include pain, bruising in the area from where the blood is taken, redness and swelling of the vein, infection, dizziness and a rare risk of fainting. These risks will vary from person to person. The healthcare staff will follow normal clinical practices to ensure sterility and safety. Study participants undergoing the blood draw will be advised to talk to their doctor about any side effects while taking part in this study. Many patients will be getting their blood drawn for non-study purposes, thus, only adverse events associated with study blood draws will be attributed to the study. Adverse events associated with colonoscopy (perforation, bleeding) are extremely rare; any adverse events associated with colonoscopy will not be attributable to the study because colonoscopy is part of standard care.

Plans for the Patients at the End of the Protocol

Patients will continue to follow their schedule of recommended screenings regardless of their participation in the study. Any patient who experiences problems from participating in this study will be provided all appropriate medical care and the study staff will follow their progress and give appropriate recommendations for on-going screening. However, no further contact with patients is anticipated during or after completion of the study (beyond potential recruitment and participation for the qualitative interview component).

10. Risks and Benefits

a. Risks to Subjects

There are minimal risks and discomforts to participating in this study. Collection of blood involves potential risk of pain or discomfort, redness, bruising or localized infection at the site of the needle stick. Patients will be instructed to alert staff for any complications resulting from the blood draw.

Patients may feel uncomfortable with questions asked during the qualitative portion of the study. We will be clear that answering all questions will be optional. There may be risks of data breach.

There are no additional risks or discomforts to patients in this study.

In the unlikely event that a patient experiences physical injury or illness because of participating in this research study, medical care will be made available at the clinical site of sample collection.

b. Potential Benefits to Subjects

Patients will not benefit directly from involvement in the study. However, the general colorectal cancer screening-eligible patient population may benefit from the ease of a blood test. Some patients may benefit from obtaining the blood test and obtaining a follow-up colonoscopy.

11. Economic Burden to Subjects

No cost will be incurred by the subjects for participation in this study.

12. Compensation to Participants

Patients will not be compensated for participation.

Patients participating in the qualitative interview will be offered a \$25 gift card as appreciation for their participation.

13. Resources Available

N/A

14. Additional Approvals

N/A

15. Drugs or Devices

N/A

16. Multi-Site Research

N/A

17. Community-Based Participatory Research

N/A

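### Does counting a blood draw as completed screening, even when no result follows, distort the primary comparison?

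*Protocol*

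**What the plan says.** The rule stands in the protocol, section 4 (Study Design), inside the sentence describing the primary analysis: "we will consider completion of the blood draw as completion of colorectal cancer screening". Section 7a (Data Analysis) gives the primary endpoint as "Colorectal cancer screening completion (incl. blood test, stool-test or colonoscopy) rate within 3 months of randomization", by study condition and by intention to treat. It does not say that a result must have been reported, so section 4 supplies the operative definition for the blood test.

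Section 7 (Study Procedures) describes what follows the draw. On transport: "The Kit will be shipped to Guardant overnight". On late samples, those beyond a 7-day limit "may be subject to cancellation per the CLIA-certified lab protocol". The report reaches the investigator "via its online portal within approximately 14 days of sample receipt". The Data Collection list in the same section includes the blood test result and any FIT result after randomisation, together with the assigned cohort. Section 5f (Consent) plans retrospective chart review for outcomes in both arms.

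**The concern.** A draw and a screening result are different events. The sample goes to an outside laboratory, the report comes about two weeks after receipt, and a late sample can be cancelled. The protocol describes neither a redraw nor a reclassification of patients whose sample yields nothing. On the wording, a patient with no information about colorectal cancer can count as a success in the primary endpoint.

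Only the intervention arm is offered the draw. Compared with a rule that requires a result, the draw rule can raise that arm's rate and cannot lower it. A reader may also take completed screening to mean that a result exists. If many draws failed, part of the reported advantage would consist of patients who were bled but not screened.

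**Working it through.** **1. Does the definition fit the question, and is it even-handed?**

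- Section 2 (Objectives) asks about screening completion in patients who did not respond to stool-test outreach. That is a question about uptake.
- Sections 4 and 5e describe blood-test non-completers as patients who agreed to take part but did not attend the draw. Completion is again something the patient does.
- Section 5b identifies FIT non-completers by failure to return the kit, which is the matching patient-side event.

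The three places agree. Nothing in the protocol requires a result for a FIT while waiving it for blood.

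**2. The plan's own figure.**

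Inputs from section 7a: 200 per arm, FIT adherence 88%, difference 8 points, stated power 91.8%. The direction (88% to 96%) is an assumption. The protocol states neither alpha nor sidedness.

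- Pooled rate: (0.88 + 0.96)/2 = 0.92.
- Standard error under no difference: √(2 × 0.92 × 0.08/200) = 0.02713.
- Standard error under the alternative: √(0.88 × 0.12/200 + 0.96 × 0.04/200) = 0.02683.
- One-sided 0.05: Φ[(0.08 − 1.645 × 0.02713)/0.02683] = Φ(1.318) = 90.6%. Exact binomial enumeration of the same test gives 91.8%, which matches the protocol.
- Two-sided 0.05: Φ[(0.08 − 1.960 × 0.02713)/0.02683] = Φ(1.000) = 84.1% (exact 85.4%), which does not match.

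The stated power therefore corresponds to one-sided 0.05 (equivalently two-sided 0.10).

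**3. Size per patient.**

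One patient credited on a draw alone, with no other test, adds 1/200 = 0.5 points, and 0.5/8 = 1/16 of the planned difference.

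**4. Break-even at the planning rates.**

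Expected completions are 0.96 × 200 = 192 and 0.88 × 200 = 176. Remove k intervention patients and apply the pooled z test, z = (difference in rates)/√(2p̄(1 − p̄)/200):

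| k removed | Completions | Difference | z | Two-sided p | One-sided p |
|---|---|---|---|---|---|
| 0 | 192 v 176 | 8.0 points | 2.95 | 0.003 | 0.002 |
| 4 | 188 v 176 | 6.0 points | 2.10 | 0.036 | 0.018 |
| 5 | 187 v 176 | 5.5 points | 1.90 | 0.058 | 0.029 |
| 6 | 186 v 176 | 5.0 points | 1.71 | 0.088 | 0.044 |
| 7 | 185 v 176 | 4.5 points | 1.52 | 0.129 | 0.065 |

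The break-even is 5 patients (5/192 = 2.6% of completions) at two-sided 0.05 and 7 patients (7/192 = 3.6%) at one-sided 0.05. To remove the whole 8 points, 0.08/0.96 = 8.3% of draws would have to yield no result.

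This is a worst case. Every intervention completion is taken to be a blood draw, none of the removed patients has another test, and no FIT is reclassified in either arm. It also takes over the 88% planning rate, although the patients are selected for not having returned a kit.

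**5. Is such a failure share indicated?**

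The only route to a missing result in the protocol is the conditional cancellation of late samples, and the same list requires overnight shipment against a 7-day limit. No cancellation or failure rate is given, so nothing in the protocol points to 2.6%, 3.6% or 8.3%.

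**6. Would a gap stay hidden?**

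Section 4 has draw completion reported among consenting intervention patients, and the Data Collection list holds the blood result. Draws without a result can be counted by subtraction from data already planned.

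**The case for a change.** The strongest opposing case accepts the rule and asks only for a check. The listed outputs (consent, acceptance, test completion, positivity, endoscopy follow-up) do not name draws without a reportable result. The draw rule works in one direction on the intervention rate, and at the planning rates a handful of patients would matter. A supportive intention-to-treat comparison that counts only resulted tests in both arms, dated by when the test was taken, would cost little because the data are collected. The protocol also does not say outright when a FIT counts as complete in the primary analysis.

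Most of these facts stand: the draw rule is explicit, a draw without a result is possible, and the supportive comparison is feasible. They do not make the plan wrong. A secondary analysis under another outcome definition, and the coding rule for a returned FIT, are details that protocols commonly leave to the statistical analysis plan. That plan is not at hand and may contain both. The upward effect on the intervention rate also does not establish a biased difference: a result-based rule could reclassify returned FITs too, so its net effect on the contrast between arms is unknown.

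**Conclusion.** The concern does not hold. The draw rule is openly stated, fits a question about screening uptake, and agrees with the patient-side way in which the protocol describes non-completion of both tests. Followed as written, the plan gives a sound answer to that question.

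The possible effect is 0.5 points per draw without a result. The break-even of 5 to 7 patients rests on the planning rates of 96% and 88%, a pooled z test, an unstated significance level and no reclassified FIT. It is not a forecast, and the protocol gives no reason to expect that many failures. The conclusion is about uptake only: the primary endpoint should not be read as the proportion of patients who obtained a screening result. A supportive result-based analysis would be a sensible addition, but its absence from the protocol is not an error.

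### Eligibility does not exclude a colonoscopy already ordered or scheduled, yet colonoscopy counts toward the primary endpoint in both arms, so the treatment difference can be diluted (minor)

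*Protocol*

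**What the plan says.** Four parts of the protocol bear on this.

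- **Appointment.** Section 5a asks for non-completers of a FIT "and have an upcoming appointment at a KPNW clinic", 2-6 weeks ahead. The inclusion list in section 5b words it as "Upcoming appointment or willing to reschedule an appointment at KPNW within 2 - 6 weeks". Neither restricts the department or the kind of visit.
- **Screening status.** Section 5b requires "Received a FIT test in the last 3-9 months yet did not return their FIT". Section 2 describes the target as evaluation "in individuals who are not up to date with CRC screening".
- **Exclusions.** Section 5b lists the do-not-contact list, "Having a legal authorized representative" and non-English speakers. Section 5c adds a recorded dementia diagnosis and the usual vulnerable groups. None concerns a colonoscopy that is ordered or scheduled.
- **Endpoint.** Section 7, Data Analysis, defines the primary endpoint as "Colorectal cancer screening completion (incl. blood test, stool-test or colonoscopy) rate within 3 months of randomization, by study condition", analysed by intention to treat. It sets no condition on the date of the order.

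Under section 5e the analyst applies the eligibility criteria to records and patients are randomized 1:1 before any contact. Under section 5f usual-care patients are covered by a consent waiver, and outcomes in both arms come from chart review.

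**The concern.** The trial asks whether offering a blood test raises screening completion over a stool-test reminder. A colonoscopy arranged before randomization is a response to neither. If it takes place within the window, that patient is a completer under either allocation and carries no information about the contrast.

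The other criteria do not screen such patients out. A colonoscopy that is booked but not done leaves the patient not up to date. An unreturned FIT is compatible with having chosen colonoscopy instead. Stratification by ever versus never screened does not capture a pending order. Because usual-care patients are not contacted for consent, no described step would identify them in that arm later.

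At stake are some loss of contrast and power, and completion rates in both arms that include procedures already arranged at entry.

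**Working it through.** **Inputs from the protocol** (section 7, sample size calculation): control rate 88%, difference 8 points (so 96% in the blood-test arm), 200 per arm, stated power 91.8%. Neither alpha nor sidedness is stated.

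**Assumed input:** p, the share of each arm that completes a pre-arranged colonoscopy within 3 months regardless of allocation. The protocol gives no value; 2%, 5% and 10% are shown.

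**Step 1: reproduce the stated power.** With the pooled normal approximation,

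power = Φ{[d - z·√(2·p̄(1 - p̄)/n)] / √([p1(1 - p1) + p2(1 - p2)]/n)},

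where d = 0.08, p̄ = 0.92 and n = 200:

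- One-sided 5% (z = 1.645): (0.08 - 1.645 × 0.02713)/0.02683 = 1.318, giving 90.6%. Exact binomial enumeration of the same uncorrected test gives 91.8%, the stated figure.
- Two-sided 5% (z = 1.960): (0.08 - 1.960 × 0.02713)/0.02683 = 1.000, giving 84.1%. Exact enumeration gives 85.4%, which does not match.

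Since the protocol does not say which test applies, both are carried forward. The missing alpha is a separate matter.

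**Step 2: timing.** The qualifying appointment falls 2-6 weeks after eligibility determination, and the endpoint is a "rate within 3 months of randomization". A procedure on that date would be expected to fall inside the window.

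**Step 3: dilution.** In each arm the observed rate is p + (1 - p) × r, where r is the rate in everyone else. Subtracting the arms, p cancels:

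difference = (1 - p) × (r2 - r1) = (1 - p) × 8 points.

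| p | Usual care | Blood test | Difference | Power, one-sided 5% | Power, two-sided 5% |
|---|---|---|---|---|---|
| 0% | 88.0% | 96.0% | 8.00 | 90.6% | 84.1% |
| 2% | 88.24% | 96.08% | 7.84 | 90.1% | 83.3% |
| 5% | 88.6% | 96.2% | 7.60 | 89.2% | 82.1% |
| 10% | 89.2% | 96.4% | 7.20 | 87.5% | 79.8% |

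Against the first row, power falls by 0.5 (one-sided) or 0.8 (two-sided) points at 2%, by 1.4 or 2.0 at 5%, and by 3.1 or 4.3 at 10%.

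**Step 4: effect on the reported usual-care rate at p = 5%.**

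- Protocol's own 88%: 0.05 + 0.95 × 0.88 = 88.6%.
- Assumed 20%: 0.05 + 0.95 × 0.20 = 24%.
- Assumed 10% and 30%: 14.5% and 33.5%.

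**Step 5: sensitivity of the power loss to the base rate.** If the same 8 points sat on a lower assumed control rate, two-sided power at p = 5% would go from 63.6% to 50.2% (control 10%), 46.5% to 39.6% (20%) or 39.3% to 34.8% (30%). Power for 8 points is already low there without any dilution. Whether 88% suits this population is a separate question.

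**The case against.** The strongest reply is that the context points to ordinary visits. Section 2 speaks of a clinical appointment at which usual-care patients are reminded about stool testing, which makes little sense if the appointment is the colonoscopy. Section 5e has staff meet patients around a clinical visit. This has force as a guide to intent, but it is not a criterion, and the analyst selects on the criteria. Even with an ordinary qualifying visit, a patient may hold a separate colonoscopy order.

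It can also be said that randomization balances these patients, that intention to treat counts them correctly, and that someone screened by colonoscopy has been screened. All of that stands: in expectation there is no bias toward either arm, and including them is coherent if the target is overall completion in the enrolled population.

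A reader might infer more than the documents support:

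- *That such patients do enter.* The protocol permits it but gives no frequency.
- *That a work-up visit or an open referral amounts to a booked endpoint.* It need not lead to a colonoscopy within 3 months.
- *That diagnostic procedures will be reported as screening uptake.* The endpoint is framed as screening completion. How indication is judged from the chart may be set out in an analysis plan not shown here.
- *That usual-care completion is overstated by one-fifth.* That ratio (24% against 20%) depends on an assumed 20% rate. At the protocol's 88% the rise is 0.6 points.
- *That the blood test is unsuitable for patients under work-up.* Nothing in the protocol addresses this.

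**Conclusion.** The gap is real and minor. The criteria allow a patient to be randomized with a colonoscopy already ordered or scheduled, and that colonoscopy would count toward the primary endpoint in either arm. The result is non-differential dilution: the contrast shrinks by the factor (1 - p) and both rates rise. At the planning rates, an assumed p of 5% turns 8 points into 7.6 and costs 1.4 to 2 points of power; at 10% the cost is 3 to 4 points.

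These sizes rest on an assumed p that is equal in both arms, on certain completion in that share, and on 88% versus 96% in everyone else. No stated figure in the protocol is wrong on this account. An analysis plan could not supply the missing exclusion, because eligibility is set in the protocol and applied before randomization.

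**What to change.** Add to the exclusions in section 5b, applied from the chart before randomization and identically in both arms: *colonoscopy already ordered or scheduled at eligibility determination*. State in sections 5a and 5b that the qualifying appointment cannot itself be a colonoscopy or its preparatory visit.

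If the sponsor prefers to keep these patients, flag them from the chart as it stood at eligibility determination, so that the flag cannot depend on allocation, and report a sensitivity analysis of the primary endpoint without them. This shows the size of the dilution but does not recover the lost power in the primary analysis.

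The cost is one eligibility line and one more filter in the weekly record pull, with a slightly smaller eligible pool if the exclusion is adopted.
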